#### **4. MILESTONES**

Milestone	Planned/Estimated date
Draft Protocol	7 March 2025
Registered with HMA-EMA catalogue	30 April 2025
Final Protocol	01 May 2025
Protocol Amendment	19 October 2025
Start of data collection	November 2025
First Interim Tables (Data through December 2025)	
 
Preliminary Version - December 2025
 
Final Version – April 2026
 

Second Interim Tables (Data through October 2026)	
 
Preliminary Version - December 2026
 
Final Version – April 2027
 

Third Interim Tables (Data through October 2027)	
 
Preliminary Version - December 2027
 
Final Version – April 2028
 

Final report (Data through when follow-up is completed on all participants)	
 
Preliminary Version - –6 months after end of data collection
 
Final Version – 12 months after end of data collection
 

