## 7.2. Study Population and Setting

The study population includes treatment-experienced, virologically suppressed (VL < 50 copies/mL) individuals who are 18 years or older and received at least one CAB+RPV LA injection with every-2 month dosing schedule, from participating clinical sites across several countries. Anticipated countries include the UK, Italy, Portugal, France, Spain, Germany, Japan, South Korea, Taiwan, Australia, Canada, and the US. Enrollment will take place as part of a participant’s standard of care visit at a participating site.

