**Retrospective Participants:**

Retrospective participants will include individuals who initiated CAB+RPV LA from January 2023 and will be followed for up to two years. Participants who have discontinued CAB+RPV LA for any reason will be included and participants who are deceased or lost to follow up will not be included. Participants who discontinue and switch to a subsequent regimen or who experience CVF will be followed-up for a minimum of 6 months and may be extended until viral load assessment is completed, with a maximum duration of 12 months.

The sampling methodology will be designed with the goal of maximising the probability that each individual treated with CAB+RPV LA will have an equal opportunity to be selected. Participants will be enrolled as they come in for a scheduled visit, however if the volume of participants at a site is large, a customized, site-specific sampling approach may be devised to achieve an efficient method of obtaining a representative sample of participants. In some sites, it is likely that all treated participants will be selected.

The study will aim to select a diverse group of medical practices to represent diversity in clinical practice settings and to support recruitment of a diverse sample of participants (e.g., prioritizing non-cisgender males, individuals aged 50 years or older, and individuals with BMI  $\geq 30$  kg/m^2).

Individuals who are viremic (VL  $\geq 50$  copies/mL) at initiation will not be included in this study. Individuals with VL results available around the time of initiation at VL  $< 50$  copies/mL will be included in the study regardless of VL levels following enrollment.

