#### 7.5. Study Size

The study will aim to enroll up to approximately 2,000 participants. Among them, it is estimated that 250 participants are already receiving CAB+RPV LA at the time of study start, and 1,750 participants will be newly initiating CAB+RPV LA.

There is no formal statistical hypothesis to be tested in these analyses. The study will be descriptive in nature and will focus on absolute effectiveness estimation. A precision calculation was performed using power analysis and sample size (PASS) software version 14 using the exact Clopper-Pearson method based on the cumulative probabilities of the binomial distribution for 1 proportion.

In order to demonstrate the estimated precision for the total sample size and also among the groups of participants already receiving and newly initiating CAB+RPV LA, Table 1 presents the precision calculations for the width of 95% confidence intervals for a range of proportions and a combination of sample sizes. It is anticipated that data from 2,000

participants are thought adequate to provide reasonable precision around a point estimate (here defined as a proportion) to meet the study objectives. With 2,000 participants, the 2-sided 95% confidence interval precision width for the estimation of virologic failure rate will range from 1.28% and 2.13% for a failure rate ranging from 2% to 6%.

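### Enrolling retrospective participants as they attend visits favours current users over people who have stopped, which conflicts with the equal-opportunity aim and can raise retrospective persistence by an amount the protocol does not fix

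*Protocol*

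**What the plan says.** Protocol section 7.2, under Retrospective Participants, says the sampling will be designed with the goal of "maximising the probability that each individual treated with CAB+RPV LA will have an equal opportunity to be selected". The default that follows is "Participants will be enrolled as they come in for a scheduled visit". The opening paragraph of section 7.2 also ties enrolment to a "standard of care visit at a participating site".

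People who have stopped are eligible: "Participants who have discontinued CAB+RPV LA for any reason will be included". Two statements soften the default. A site-specific sampling approach may be devised where a site has a large volume, and at some sites all treated participants are expected to be selected.

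Section 7.5 sizes the group: "it is estimated that 250 participants are already receiving CAB+RPV LA at the time of study start", with 1,750 new initiators making up the rest of about 2,000. Section 7.3.2 gives 53 to 67 days as the on-time window for a continuation injection. It defines persistence, a primary outcome, as the proportion still on the regimen at time of analysis, at 6, 12 and 24 months, and at study end. Section 4 places the start of data collection in November 2025 and the interim data cuts in December 2025, October 2026 and October 2027.

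The protocol states no length for the retrospective enrolment period, no visit interval for people who have stopped, and no count of eligible people who were not enrolled by treatment status. Section 7.7.1.3 plans no sensitivity analyses, and section 7.9 does not list this selection as a limitation.

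**The concern.** When people are recruited at visits during a limited period, the chance of selection rises with visit frequency. Here visit frequency depends on treatment status: current users return about every two months for injections, and people who have stopped do not. Treatment status is also what persistence and discontinuation measure, so the route into the sample is linked to the primary outcome.

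This acts among people who are alive, in care and eligible at the same site. It is therefore separate from the exclusion of people who died or were lost to follow-up. At stake are retrospective persistence (upward), discontinuation and reasons for stopping (under-represented), and possibly CVF (downward). One of the two CVF routes in section 7.3.2 requires discontinuation within 4 months of a viral load of at least 200 copies/mL, so people who stopped after failure would be among those missed.

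**Working it through.** **The plan's own figures.** The only calculated figures are the exact (Clopper-Pearson) interval widths in section 7.5. They reproduce: at N = 250, 0.0395 for 2% and 0.0631 for 6%; at N = 2,000, 0.0128 and 0.0213. The protocol gives no selection probability or expected persistence, so the size of this effect can only be illustrated.

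**Inputs from the protocol.** Injection interval about 60 days (midpoint of 53 to 67); 250 retrospective and 1,750 prospective participants; the dates in section 4.

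**Assumptions, not in the protocol.** True share stopped d = 20% or 30%; interval v between visits after stopping = 90, 120 or 180 days; retrospective enrolment window W = 60 days, taken from the gap between the start of data collection and the first data cut.

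**Selection model.** With visits spread evenly, the chance of attending within the window is min(1, W/interval). For W = 60 this is 1 for current users and p = 60/v for people who have stopped. The enrolled share stopped is d·p / (d·p + 1 − d).

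| v (days) | p | d = 20%: share stopped | reads as on treatment (true 80%) | d = 30%: share stopped | reads as on treatment (true 70%) |
|---|---|---|---|---|---|
| 90 | 0.667 | 0.133/0.933 = 14.3% | 85.7% | 0.200/0.900 = 22.2% | 77.8% |
| 120 | 0.500 | 0.100/0.900 = 11.1% | 88.9% | 0.150/0.850 = 17.6% | 82.4% |
| 180 | 0.333 | 0.067/0.867 = 7.7% | 92.3% | 0.100/0.800 = 12.5% | 87.5% |

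**When the effect vanishes.** If v = 60, p = 1 and the bias is zero. If W is at least v and every attender is taken, both chances are 1 and the bias is again zero. In between it shrinks: at d = 20% and v = 180, W = 90 gives p = 0.5 and a reading of 88.9%; W = 180 gives 80%.

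**Early timepoints.** The table describes current status, which corresponds to persistence at time of analysis. For month 6, assume 5% had stopped by then and 20% overall. The enrolled share stopped by month 6 is 0.05p / (0.20p + 0.80), which is 0.0333/0.9333 = 3.6% at p = 0.667 and 0.0167/0.8667 = 1.9% at p = 0.333. Month-6 persistence reads 96.4% to 98.1% against 95%, an error of +1.4 to +3.1 points.

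**Against sampling error.** At N = 250 and 80%, the exact 95% interval runs from 74.5% to 84.8%, a half-width of about 5.1 points. The illustrated errors of +5.7 to +12.3 points exceed it.

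**Pooled effect.** The retrospective share is 250/2,000 = 12.5%. At d = 20%, 0.125 × 5.7 = +0.7 and 0.125 × 12.3 = +1.5 points, against a pooled half-width of about 1.8 points.

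**Interim tables.** A prospective participant enrolled in November 2025 reaches month 6 no earlier than May 2026, month 12 no earlier than November 2026, and month 24 no earlier than November 2027. Set against the three data cuts, all month-24 results in all three interim tables, all month-12 results in the first two and all month-6 results in the first come from retrospective participants alone.

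**The case against.** Section 7.2 states a goal and a default, with the sampling detail still to be designed. It expressly admits people who have stopped, allows a tailored approach at large sites and expects full capture at some. Where everyone treated is taken, this bias is zero. A reader might infer that current users are much likelier to be enrolled, or that the equal-opportunity aim is defeated. The documents do not support that: both readings need a visit interval after stopping and an enrolment window, and neither is stated.

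Two further inferences also fail. The 60 days is the gap to the first data cut, and nothing says retrospective enrolment closes then. The 250 is an estimate and not a quota, so the text does not show frequent attenders taking places from others. Dilution is also real: the 1,750 prospective participants enrol before their first injection and are unaffected. The effect on CVF is uncertain, because people may be seen more often soon after failure.

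All of this limits the size. It does not remove the conflict. Eligibility is not equal probability. The tailored approach is optional and triggered by volume, not by treatment status. Full capture is expected only at some sites. The protocol does not commit to a window long enough to make the chances equal, and dilution does not help interim timepoints that no prospective participant can have reached.

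**Conclusion.** The point holds in a limited form. The visit-based default conflicts with the stated equal-opportunity aim. Where people who have stopped attend less often than every two months and the enrolment period is short relative to their visit interval, it can only push retrospective persistence up and discontinuation down. CVF may be pushed down; no figure can be given.

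The amount cannot be determined from the protocol and may be zero. The 85.7% to 92.3% range against 80% rests on an assumed 20% stopped, a 60-day window and visits every 90 to 180 days after stopping. It is an illustration of the early enrolled group, not a forecast of the final result. The final pooled estimate would move little (about +0.7 to +1.5 points on those inputs). The exposure lies in retrospective-only results, above all the later timepoints in the interim tables, from which section 11 plans abstracts. It is worth correcting because the remedy is cheap; it does not undermine the prospective cohort.

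**What to change.** In section 7.2, Retrospective Participants, replace the attendance default with a list. Each site lists everyone with a first CAB+RPV LA injection from January 2023, on or off treatment, and invites all of them or, where volume is large, a random draw. A draw in order of first-injection date would not serve, since unless the list is exhausted it selects by start date.

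Enrolment and consent can stay at the standard of care visit, provided retrospective enrolment remains open for at least the longest routine visit interval and a drawn person is not replaced by the next attender. Each site logs the numbers eligible, approached and enrolled by on/off status. Persistence, discontinuation and CVF are reported separately for retrospective and prospective participants, in the interim tables as well as the final report.

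The cost is a site list and a log, slower filling of the retrospective group, and fewer retrospective participants in the first interim tables.

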**7.2.1 Inclusion criteria:**

- Diagnosis of HIV-1
- Aged  $\geq 18$  years at time of CAB+RPV LA injection
- Treatment experienced
- VL < 50 copies/mL at initiation
- Initiated every 2 month dosing CAB+RPV LA
  - For prospective participants, study enrollment should occur prior to the first CAB+RPV LA injection, either during the OOLI phase, if applicable, or directly before their first CAB+RPV LA injection for those on the DTI pathway
  - For retrospective participants, individuals who initiated CAB+RPV LA from January 2023 will be enrolled

**7.2.2 Exclusion Criteria**

- Received CAB+RPV LA regimen as part of a randomized controlled clinical trial
- Treatment naïve
- VL  $\geq 50$  copies/mL at initiation
- Individuals with prior virologic failure to agents of NNRTI or INSTI class (if data is available)

**7.3. Variables**

**7.3.1. Exposure Definitions**

All users of CAB+RPV LA regimen treated per the approved prescribing information or summary of product characteristics for CAB+RPV LA will be included in the study.

**7.3.2. Outcome Definitions**

Endpoint	Definition
Primary	
Persistence	
 
▪ Proportion of participants still on CAB+RPV LA at time of analysis, after 6, 12, and 24 months of use and at study end
 

Discontinuation	
 
▪ Proportion discontinuing after last injection:                             
 
○ Date of discontinuation will be the date of the last injection prior to:                                     
 
▪ no injections and no documentation of oral bridging for more than 127 days after any injection.
 
 
 
 
 

Endpoint	Definition																	
	
 
▪ Physician confirmed treatment switch from CAB+RPV LA to another ARV regimen
 
▪ Physician confirmed treatment stop of CAB+RPV LA
 
▪ Median time to discontinuation
 
▪ Proportion of participants who discontinued and reinitiated the regimen within 6 months from discontinuation
 
																	
Adherence	
 
▪ Adherence to the dosing schedule will be assessed as the proportion of participants who received their injections within the +/- 7-day dosing window relative to their target treatment date as detailed below (see table: Days After Last Injection)
 
▪ Non-adherence to the dosing schedule will be assessed as follows:                             
 
○ Describe the proportion of participants who received CAB+RPV LA more than 7 days earlier or later than their target treatment date                                     
 
▪ Mean/median (range) number and time from target injection date to actual injection date of early or delayed injections and number of participants with 1, 2, 3 and ≥4 early or delayed injections
 
 
 
○ Describe the proportion of participants who missed one consecutive injection with and without taking daily oral therapy or any other oral ARV regimen while not on CAB+RPV LA                                     
 
▪ Mean and median number of injections missed, time from target injection date to actual injection date, and number of participants with 1, 2, 3 and ≥4 missed injections
 
 
 
 
 
 
  
 	Days after last injection	
 
 	Q2M 2nd initiation injection	Q2M continuation injection	
   
 On-time	23-37	53-67	
 
 Late	38-67	68-127	
 
 Delayed (Short delay)	38-67	68-97	
  
				Days after last injection			Q2M 2 nd initiation injection	Q2M continuation injection	On-time	23-37	53-67	Late	38-67	68-127	Delayed (Short delay)	38-67	68-97
	Days after last injection																	
	Q2M 2 nd initiation injection	Q2M continuation injection																
On-time	23-37	53-67																
Late	38-67	68-127																
Delayed (Short delay)	38-67	68-97																

Endpoint	Definition		
	Long delay (requiring re-initiation)	NA	98-127
	Requiring re-initiation/ Discontinuation	>67	>127
CVF	Proportion of participants with: 
 
▪ 2 consecutive HIV RNA VL <math>\geq</math> 200 copies/mL prior to/by assessment timepoint
 
OR
 
▪ 1 HIV RNA VL level <math>\geq</math> 200 copies/mL prior to/by assessment timepoint followed by core agent/regimen discontinuation within 4 months of HIV RNA VL level <math>\geq</math> 200 copies/mL
 
		
Virologic suppression	
 
▪ Proportion of participants with VL measurement <math><</math> 50 copies/mL during follow-up
 
		
Non-response	
 
▪ Not achieving re-suppression after CVF, consisting of VL <math>\geq</math>50 copies/mL following CVF with no VL of <math><</math>50 copies/mL following CVF
 
		
Secondary			
Injection site reactions	
 
▪ Proportion of participants with documented diagnostic code/diagnosis of injection site reaction or nodules attributed to administration of CAB+RPV LA
 
▪ Proportion of participants with Division of AIDS grading 1-4 to classify severity
 
		
Hypersensitivity reactions	
 
▪ Proportion of participants with documented diagnosis of Hypersensitivity, anaphylactic reaction, allergic reaction or drug allergy to CAB+RPV LA
 
▪ 2 or more events are reported from 2 or more of the following groups of signs/symptoms:                             
 
○ Rash, fever, gastrointestinal symptoms (nausea, vomiting, diarrhea, abdominal pain), constitutional symptoms (lethargy, fatigue, malaise, myalgia, arthralgia, general ill feeling) respiratory symptoms (dyspnea, sore throat, cough, chest x-ray changes, predominantly infiltrates, which can be localized)
 
 
 
▪ Cases where there is a negative rechallenge with CAB+RPV LA
 
▪ Cases where symptoms resolved (or did not worsen/result in withdrawal from the study)
 
		
Emergent resistance	
 
▪ Proportion of participants with resistance and and proviral DNA testing at discontinuation/CVF.
 
		

Endpoint	Definition
	
 
▪ Proportion of participants with history of resistance and proviral DNA testing prior to discontinuation/CVF.
 
▪ The proportion of participants tested with any resistance mutation will be reported at discontinuation/CVF and history of prior to discontinuation/CVF, as will mutations associated with reduced susceptibility at the class-level and drug-level                             
 
○ All mutations will be reported; specific resistance mutations of interest to CAB+RPV LA can be highlighted and identified using the International Antiviral Society mutations list and Stanford HIV drug resistance database.
 
 
 

Patient-reported outcomes	
Reasons for initiating CAB+RPV LA	
 
▪ Descriptive summary of bespoke questionnaire (2 items) completed at baseline
 

Baseline adherence	
 
▪ Descriptive summary of bespoke questionnaire (7 items) completed at baseline
 

HIV health-related quality of life	
 
▪ Descriptive summary of WHOQOL-HIV BREF (31 items) completed at baseline, month 12 and discontinuation, if applicable
 

HIV treatment-related worries and stigma	
 
▪ Descriptive summary of HIV Treatment-Related Worries (HRW; 4 items) completed at baseline, month 12 and discontinuation, if applicable
 

Treatment-related benefits	
 
▪ Descriptive summary of bespoke questionnaire (7 items) completed at month 12, if applicable
 

Treatment satisfaction	
 
▪ Descriptive summary of HIVTSQs (12 items) completed at baseline and month 12, if applicable
 

Change in treatment satisfaction	
 
▪ Descriptive summary of HIVTSQc (12 items) completed at month 12, if applicable
 

Treatment preference	
 
▪ Descriptive summary of bespoke questionnaire (3 items) completed at month 12, if applicable
 

Reasons for missed injection(s)	
 
▪ Descriptive summary of bespoke questionnaire (4 items) completed at month 12, if applicable
 

Reasons for discontinuation	
 
▪ Descriptive summary of bespoke questionnaire (3 items) completed at discontinuation
 

Social determinants of health (SDoH)	
 
▪ Descriptive summary of bespoke questionnaire (7 items) completed at baseline and month 12, if applicable
 

ARV = antiretroviral; CAB = cabotegravir; CVF = confirmed virologic failure; HIV = human immunodeficiency virus; HIVTSQs = HIV Treatment Satisfaction Questionnaire status version; HIVTSQc = HIV Treatment Satisfaction Questionnaire change version; LA = long-acting; RPV = rilpivirine; VL = viral load; WHOQOL-HIV BREF = World Health Organization Quality of Life-Human Immunodeficiency Virus BREF.

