## 6. RESEARCH QUESTION AND OBJECTIVE(S)

### 6.1. Primary Objective

The overall objective of this global study is to describe participant characteristics and assess clinical outcomes and patient-reported outcomes among people with HIV who receive CAB+RPV LA regimen.

1. To describe baseline demographics, clinical characteristics and patterns of use among participants receiving CAB+RPV LA
  - Descriptive analysis of study population by baseline demographic and clinical characteristics
  - Monitor for use of OOLI
2. To assess the persistence, discontinuation, and adherence among participants receiving CAB+RPV LA
  - Persistence: Proportion of participants still on CAB+RPV LA at time of analysis, after 6, 12, and 24 months of use and at study end
  - Proportion of participants discontinuing the regimens of interest will be assessed
    - a. Reasons for discontinuation will be assessed

- Non-adherence to the dosing schedule will be assessed by:
  - a. Estimating the number of participants who missed 1 or more consecutive injections without taking daily oral bridging therapy or any other oral ARV regimen while not on CAB+RPV LA and estimating the mean and median number of injections missed during a 12-month period
  - b. Estimating the number of participants who received the injections more than 7 days earlier or later than their scheduled injection visit and median time from target injection to actual injection date of early delayed injections
  - c. Estimating the number of participants who missed 1 or more consecutive injections without taking daily oral bridging therapy or those who received the injections more than 7 days earlier or later than their scheduled injection visit (combined group A or B) and describe individual characteristics for the participants who are non-adherent.
  
- 3. To assess virologic effectiveness (i.e., proportion of participants experiencing virologic suppression and CVF) among participants receiving CAB+RPV LA regimen
  - Estimate overall number and proportion of participants with CVF and time to CVF (months)
  - Estimate the proportion of participants with CVF during the first 6 months after initiation of CAB+RPV LA
  - Estimate the proportion of participants with CVF 6, 12, and 24 months after initiation of CAB+RPV LA
  - Assessment of virologic suppression among participants on CAB+RPV LA regimen during first 6 months and at 6, 12, and 24 months after initiation of the regimen

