### Prospective Participants:

[figure not shown]
Prospective participants will include individuals enrolled from November 2025 until study size is reached. Participants will be enrolled prior to their first CAB+RPV LA injection, either during the optional oral lead-in (OOLI) phase, if applicable, or directly before their first CAB+RPV LA injection for those on the direct-to-injection (DTI) pathway. The baseline survey will be administered before the first CAB+RPV LA injection. The participants will be followed for a minimum of two years, unless they withdraw from the study, are lost to follow-up, or pass away. Participants who discontinue and switch to a subsequent regimen or who experience CVF will be followed-up for a minimum of 6 months and may be extended until viral load assessment is completed, with a maximum duration of 12 months.

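### Minor: discontinuation after the first injection has two gap limits (>127 and >67 days), and persistence at data cuts misses gap-only stops less than 128 days old

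*Protocol*

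**What the plan says.** Section 7.3.2 lists three routes to discontinuation, all dated to the last injection before the event. The first is a gap: "no injections and no documentation of oral bridging for more than 127 days after any injection". The others are a physician-confirmed switch and "Physician confirmed treatment stop of CAB+RPV LA". The section also reports "Proportion of participants who discontinued and reinitiated the regimen within 6 months from discontinuation".

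The table of days after the last injection sits under Adherence in the same section. Its row "Requiring re-initiation/ Discontinuation" gives >67 days for the second initiation injection and >127 days for continuation injections. A separate long-delay row, also marked as needing re-initiation, is 98-127 days for continuation injections and not applicable to the second initiation injection.

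Persistence is "Proportion of participants still on CAB+RPV LA at time of analysis, after 6, 12, and 24 months of use" and at study end (Sections 6.1 and 7.3.2). Extra follow-up is tied to a switch or CVF: "Participants who discontinue and switch to a subsequent regimen or who experience CVF will be followed-up for a minimum of 6 months", to a maximum of 12 months (Section 7.2). Retrospective participants "initiated CAB+RPV LA from January 2023 and will be followed for up to two years"; prospective participants have at least two years. Interim tables use fixed calendar cuts (Section 4), abstracts are planned from the interim analysis (Section 11), and Kaplan-Meier is optional (Section 7.7.1.1).

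**The concern.** Persistence and discontinuation are primary outcomes, and the same treatment history can be labelled in two ways.

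First, the gap rule in the text applies after any injection, so it includes the first. The table attaches a discontinuation label to a shorter gap for that injection. A participant who comes back on day 100 after injection 1 is persistent under one limit. Under the other, the same participant is a discontinuation and also a re-initiation within 6 months.

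Second, a participant who stops silently cannot be recognised as stopped until 128 days after the last injection, and the stop is then dated back to that injection. A plain proportion still on treatment at a data cut therefore counts as persistent some people whom the same definition will later date as stopped before the cut. The error runs in one direction.

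**Working it through.** **Part 1: which limit applies after injection 1.** The on-time windows 23-37 and 53-67 are 30 ± 7 and 60 ± 7, so the targets are 30 and 60 days. The limits can be built in two ways:

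- 2 × 30 + 7 = 67 and 2 × 60 + 7 = 127. This makes >67 the counterpart of >127, i.e. discontinuation.
- 30 + 37 = 67 and 60 + 37 = 97. This makes >67 the counterpart of >97, which the table calls re-initiation.

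The arithmetic does not decide between them. The consequences for a participant without bridging or a physician-confirmed stop after injection 1 are:

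| History after injection 1 | Limit >127 | Limit >67 |
|---|---|---|
| Returns by day 67 | persistent | persistent |
| Returns on days 68-127 | persistent | discontinued, then re-initiated within 6 months (127 < 183 days) |
| Data end on days 68-127, no return | not yet classified | discontinued |
| Never returns, day 128 observed | discontinued, dated to injection 1 | the same |

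The protocol gives no share for the middle rows. Each 1% of 2,000 who return in that band is 0.01 × 2,000 = 20 participants, or 1.0 point on discontinuation. With uniform enrollment from 1 November 2025, 60 of 365 entry dates (16%) put the October 2026 cut in the band, but only those without a second injection are affected.

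**Part 2: size of the overstatement.** The protocol gives no discontinuation rate. Assumptions: a share D = 10%, 20% or 30% discontinues by day 730 at a constant rate, so S(t) = exp(t × ln(1 − D)/730); 20% of stops are gap-only; prospective entry is uniform from 1 November 2025; injection data are complete to the cut.

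For a participant with f days of follow-up, gap-only stops dated in the last 127 days are invisible. The overstatement is 0.2 × [S(max(0, f − 127)) − S(f)], averaged over entry dates (365 for October 2026, 730 for October 2027). A stricter count takes only those already overdue. On continuation dosing the on-time window runs to day 67, so S(f) is replaced by S(max(0, f − 67)). For month 24 with data ending at day 730, the expression is 0.2 × [S(603) − S(730)], or S(603) − S(663) for overdue participants only.

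| Percentage points, 20% gap-only | D = 10% | D = 20% | D = 30% |
|---|---|---|---|
| Time of analysis, October 2026 | 0.30 | 0.61 | 0.95 |
| – overdue only | 0.12 | 0.26 | 0.40 |
| Time of analysis, October 2027 | 0.32 | 0.64 | 0.97 |
| – overdue only | 0.14 | 0.29 | 0.44 |
| Month 24, data end at day 730 | 0.33 | 0.63 | 0.90 |
| – overdue only | 0.16 | 0.30 | 0.43 |
| Month 24 pooled, only the 250 retrospective truncated (× 250/2,000) | 0.04 | 0.08 | 0.11 |

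Fixed-time persistence at the interims is affected less. At the October 2026 cut, 128 of 182 eligible prospective entry dates (70%) lack full run-out for 6-month persistence, giving 0.1-0.4 points. If the 250 retrospective participants are added and 1,750 enroll evenly over two years (2.397 per day), the share is 307/(436 + 250) = 45% and the effect 0.08-0.26 points. At the October 2027 cut the 12-month figures are 128 of 365 (35%) and 0.1-0.2 points.

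**Comparison with sampling error.** The exact Clopper-Pearson method reproduces Table 1 of Section 7.5 (N = 2,000: widths 1.28% at 2% and 2.13% at 6%). The same method at 10-30% gives 95% half-widths of 1.3-2.0 points for N = 2,000 and 3.9-5.9 points for N = 250.

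**The case against.** On Part 1, the Discontinuation text is the operative definition and the table is called up only for adherence. The row label joins two states, and because the long-delay cell is not applicable to the second initiation injection, >67 is the only place where that column can show re-initiation. This reading is plausible, perhaps the likelier one. The protocol does not state it, however, and the row's continuation entry equals the discontinuation limit exactly, so the ambiguity stands.

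On Part 2, a censoring or data-maturity rule is often left to the SAP, and Section 7.7.1.1 mentions estimators that handle right-censoring. That carries weight, and it is one reason for the low grade. But the protocol itself fixes the 127-day gap, the back-dating, the plain proportion at the time of analysis and the calendar cuts. Kaplan-Meier with censoring at data end would still miss stops less than 128 days old.

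A reader might infer a much larger bias. If every stop were gap-only, the same formulas give 1.5-4.8 points at the interims and 1.7-4.5 at month 24. The documents do not support that. Section 5 treats a move to another suppressive regimen as essential after stopping, so a confirmed switch is the expected route. Retrospective participants who were lost to follow-up are not included (Section 7.2), and sites are queried about unclear records (Sections 7.7.1.2 and 7.8.1). In addition, 67 of the 127 days (53%) pass before a continuation dose is late.

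**Conclusion.** The point holds as a minor one.

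Part 1 is an unresolved wording conflict in a primary outcome definition. It changes labels only for participants in the day 68-127 band after injection 1. It would be wrong to infer that the discontinuation analysis as a whole is contradictory: continuation injections have one limit, and those who never return are classified and dated identically under both.

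Part 2 is a small overstatement in one direction. It is about 0.3-1.0 points for time-of-analysis persistence in prospective participants, roughly half that or slightly less if only overdue participants count, and zero if every stop is physician-confirmed. At the final month-24 analysis the pooled effect is about 0.1 point or less, far below the half-width of 1.3-2.0 points. That last figure assumes prospective data run past month 24, as the two-year minimum allows; if they too ended at day 730, it would be 0.3-0.9 points. All sizes rest on the assumed 10-30% discontinuation, the 20% gap-only share, uniform entry and injection data complete to the cut. Since the eCRF is completed at enrollment, annually and at study end (Section 7.4), the last assumption may not hold at an interim.

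**What to change.** 1. In Section 7.3.2, state that more than 67 days after the first injection means re-initiation only, and that more than 127 days is discontinuation after any injection. Alternatively, put the >67-day limit after the first injection into the Discontinuation text. The first option leaves the primary definition unchanged.
2. At interim cuts and at study end, report persistence as of 128 days before data end, counting only stops dated by then: Kaplan-Meier with administrative censoring at that date. Take data end as the last date to which the participant's injections were abstracted.
3. For retrospective participants, read the chart 128 days past month 24 (730 + 128 = day 858) where the record is available.

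The cost is protocol wording, about four months of extra chart reading for injection dates in the retrospective group, and interim persistence that refers to a date about four months before the cut.
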